To this end, the proposed study seeks to measure the efficacy of three digital health technologies to improve the management of care and quality of life of patients with congestive heart failure (CHF). Patients who are enrolled in a general heart failure clinic within the Yale health system specializing in the treatment of heart failure will be eligible for the study and approached for consent. Subjects will be randomized into either a control (usual care) group, or to one of three intervention arms assessing three digital health technologies (described below). These technologies are either devices that measure and relay to the provider key physiological parameters in patients with CHF or are data-driven communication applications that provide either live or automated personalized coaching. All technologies can be used on a daily basis by patients at home and are meant to both increase patient engagement in the management of their disease as well as provide physicians with additional information that can be used in the clinical decision-making process. Patients will be followed for 6 months. Our primary outcome will assess changes in quality of life, while secondary outcomes will measure various parameters of clinical efficiency, patient and provider satisfaction, and patient outcomes (i.e. mortality, hospital visits, etc).

4. Research Plan:

[figure not shown]
Study Overview:

This study will be an unblinded, 4-arm parallel group, randomized controlled trial designed to determine the efficacy of three digital health products versus usual care in improving quality of life metrics in patients with congestive heart failure (CHF). This will be a joint project between Yale's Program of Applied Translational Research, Boehringer Ingelheim (BI), and Medullan Inc. While this protocol has been developed together with BI and Medullan, and these third parties will contribute to data collection and storage, all decisions regarding data analysis, presentation and publication reside with the Yale investigators.

Patients with CHF who are enrolled at one of several outpatient clinics with the Yale New Haven Health system specializing in the treatment of heart failure will be eligible for this study. These clinics are located across the state of Connecticut, in New London, Norwich, North Haven, New Haven, Greenwich, Trumbull and Bridgeport, allowing us to capture a broad and diverse patient population.

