While patients are typically followed for approximately three months in several of these heart failure specialty clinics, this is not always the case. Even when patients have continued visits past the three month point, patients may still not have optimized care. We will reach out to any eligible patient within one month of a visit to the clinic, regardless of the length of time they have been attending clinic visits. Should we not enroll a patient during this initial call, we will continue to attempt to enroll either until a patient declines consent or until they are no longer within a month of a clinic visit.

Subject Randomization and Intervention

At this point, all consented patients will be enrolled and randomized, via a stratified permuted block randomization scheme, to one of the 4 study arms. An independent statistician will create randomization lists stratified by clinic.

Our study flow is as follows:

Three of the four study arms will be intervention groups where patients will be randomized to receive one of three digital health devices or experiences designed to enhance patient care, reduce symptoms and improve disease management, provide health coaching, and/or detect abnormalities in patients living with CHF, and overall improve the quality of life for this patient population.

Patients in each of these three groups will be encouraged to interact with their device on a daily basis. It is important to note that no formal protocol is being mandated for any of the devices (for example, patients will not be obligated to step on the BodyPort scale everyday as part of a specified protocol). They will be given information about the product, what information it provides, and how it can be helpful for them, and then will simply be encouraged to use it regularly, but may use it as often or as little as they like.

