- Patients will receive monthly calls from the clinic, regardless of randomization status, to track progress, assess engagement with products, and answer any questions.

Day 180

- Patients will be asked to complete a final electronic visit with study coordinators for study close-out. They will also be mailed a return-labeled envelope to return the digital health product. During this visit, patients will work with study coordinators and be asked to fill out final assessments electronically, including:
 - A health and technology literacy survey, to track progress over the course of the study
 - A KCCQ questionnaire to track any changes over the course of the study as a measure of the primary outcome
 - o A medication adherence survey to track changes from baseline
 - A product satisfaction survey (intervention groups only), to determine a Net Promoter Score (NPS) that measures satisfaction with the digital health product
 - A usability survey (intervention groups only), which assesses user friendliness, frequency of use, product satisfaction, and perceived impact of the product.
- Study coordinators will collect any final data needed and answer any remaining questions, and patients will complete their participation in the study.

The study timeline for an enrolled patient is as follows:

Clinician Data Collection

An important aspect of our study is to determine whether the digital health products enhance clinical efficiency and reduces physician burden. At the end of the study, we will ask participating clinicians to complete an anonymous survey that assesses physician satisfaction with the products, ease of use, effect on workload and efficiency, and contribution to clinical-decision making.

Outcomes

Our primary outcome is the rate of improved quality of life of enrolled patients after 90 days as measured by the Kansas City Cardiomyopathy Questionnaire (KCCQ), which will be given to patients prior to enrollment, at the 90 day mark, and after study completion (day 180). The KCCQ is a standardized 23- question instrument that combines aspects of physical functions, symptoms (frequency, severity, and recent changes), social function, self-efficacy, and quality of life into a single summary score on a scale of 0 to 100, giving a sensitive and specific measure of quality of life for heart failure patients.

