 - Risk of loss of confidentiality: Data collected both from patient visits/assessments/surveys and abstracted from the medical record will be de-identified and stored on RedCap and on a secure HIPAA-compliant central server within the Program of Applied Translational Research. The server is only accessible from within the Yale intranet (or via VPN remotely) and additionally requires separate logon username and password. No PHI will be included in analysis or publication. All analyses will proceed on this server alone.

We will maintain a linking file in a separate location that will allow for future linking of de-identified data to protected health information (PHI) for the purpose of potential future studies. Studies that require the use of PHI (for example, linking patient info to national outcomes databases) will require approval of both the manuscript and executive committees and a separate IRB approval.

We plan to share non-aggregate de-identified data with Medullan under with the appropriate data sharing agreements. We will provide periodic transfer of this data via encrypted secure file transfer.

- Risk of physician burden: We have strived to create a study in which physician burden is minimized. Additional clinic visits outside of usual care are minimized, and physicians are expected to manage patient care at their own discretion. The study devices were designed to increase clinical efficiency rather than hamper it, and one of our secondary outcomes is to assess provider satisfaction with the products and usability so that we can better understand how these technologies have helped or hindered their provision of care. Additionally, this risk will be mitigated in part as there will be a technical support hotline (independent of physician involvement) maintained by Medullan, inc to address technical issues with the device or software interventions. Support staff working for Medullan are trained to escalate issues that prove to be medical to the supervising physician.

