The principal investigator is responsible for monitoring the data, assuring protocol compliance, and conducting the safety reviews bi-monthly. During the review process the principal investigator will evaluate whether the study should continue unchanged, require modification/amendment, or close to enrollment.

The principal investigator or the Institutional Review Board (IRB) have the authority to stop or suspend the study or require modifications. We will conduct an internal interim analysis at 50% recruitment to assess for efficacy, as described below.

This protocol presents minimal risks to the subjects and Unanticipated Problems Involving Risks to Subjects or Others (UPIRSOs), including adverse events, are not anticipated. In the unlikely event that such events occur, Reportable Events (which are events that are serious or life-threatening and unanticipated (or anticipated but occurring with a greater frequency than expected) and possibly, probably, or definitely related) or Unanticipated Problems Involving Risks to Subjects or Others that may require a temporary or permanent interruption of study activities will be reported immediately (if possible), followed by a written report within 5 calendar days of the Principal Investigator becoming aware of the event to the IRB (using the appropriate forms from the website) and any appropriate funding and regulatory agencies. The investigator will apprise fellow investigators and study personnel of all UPIRSOs and adverse events that occur during the conduct of this research project through regular study meetings and/or via email as they are reviewed by the principal investigator. The protocol's research monitors, including study sponsors, funding and regulatory agencies, and regulatory and decision-making bodies will be informed of all adverse events within 5 days of the event becoming known to the principal investigator.

d. For multi-site studies for which the Yale PI serves as the lead investigator: N/A

13. Statistical Considerations: Describe the statistical analyses that support the study design.

Baseline comparisons across the study arms will be conducted with chi-square tests for categorical variables, applying the Maentel-Haenszel correction for stratification by clinic site. Continuous variables will be compared using the Van-Elteren test for continuous, non-parametric variables and stratified t-tests for normally distributed variables.

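### The interim efficacy analysis is internal to the investigators of an unblinded trial with a patient-reported endpoint, and nothing limits who sees its result

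*Combined protocol and SAP*

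**What the plan says.** Section I, item 4 (Study Overview) gives the design: "This study will be an unblinded, 4-arm parallel group, randomized controlled trial". Under Outcomes in the same item: "Our primary outcome is the rate of improved quality of life of enrolled patients after 90 days", measured with the KCCQ.

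Section I, item 12 (Data and Safety Monitoring Plan) assigns oversight: "The principal investigator is responsible for monitoring the data, assuring protocol compliance, and conducting the safety reviews bi-monthly". On stopping: "The principal investigator or the Institutional Review Board (IRB) have the authority to stop or suspend the study or require modifications". It then introduces the interim: "We will conduct an internal interim analysis at 50% recruitment to assess for efficacy". Item 13 (Statistical Considerations) adds the rule: a look at 50% enrollment, an efficacy stop at p < 0.0006, and a final threshold of 0.016.

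Study Overview also states that "all decisions regarding data analysis, presentation and publication reside with the Yale investigators". One independent statistical role appears, under Subject Randomization and Intervention: "An independent statistician will create randomization lists stratified by clinic". No other duty is given to that person.

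No section says who computes the interim, which records enter it, who receives the result or what is withheld. The communication to study staff described in item 12 concerns adverse events and unanticipated problems, not efficacy.

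**The concern.** Blinding gives no protection here, and the endpoint is what patients say about themselves. Several things that could influence those answers remain in the study team's hands after the interim:

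- Device use is encouraged rather than mandated (Subject Randomization and Intervention).
- For all three products, the data that trigger a provider alert may be revised as the study proceeds (product descriptions in item 4).
- Coordinators administer the KCCQ at clinic visits, work with patients on it at days 90 and 180, and may take the final surveys by telephone (Patient Follow-Up and Data Collection; patient timeline).
- Monthly calls after day 90 ask about engagement with the product.
- Some investigators may meet participants in their own practice (Section III, item 4).

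Comparing the final p-value with 0.016 assumes that answers given after the interim arise in the same way as those given before it. If a known trend changed encouragement, alerting or survey administration, the later treatment contrast would include that change, and no stopping boundary corrects for it.

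**Working it through.** **1. The plan's own sample size.** Inputs from item 13: difference 10, SD 11.8, alpha 0.017, power 90%. Sidedness is not stated; two-sided is assumed because it reproduces the figure.

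n per arm = 2(z₀.₉₉₁₅ + z₀.₉₀)² × 11.8² / 10² = 2 × (2.387 + 1.282)² × 1.392 ≈ 37.5, so 38. The t-based version needs 39, and 40 gives power 0.909. The stated 40 reproduces. A one-sided test would give 33.

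**2. The boundaries.** With looks at information fractions 0.5 and 1 (correlation √0.5), two-sided thresholds of 0.0006 and 0.016 spend 0.0162 per comparison, or 3 × 0.01624 = 0.0487 over three. Alpha is controlled. The issue is possible bias, not the nominal error rate.

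**3. Is the trial likely to continue after the look?** Half of 200 is 100 patients, 25 per arm.

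- SE = 11.8 × √(2/25) = 3.34.
- Two-sided p < 0.0006 needs |z| > 3.43, an observed difference of 3.43 × 3.34 ≈ 11.5 points.
- If the true difference is 10, z is centered at 10 / 3.34 = 3.00, and the chance of crossing is 1 − Φ(3.43 − 3.00) ≈ 0.33.

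For any one comparison, not crossing is the likelier outcome even at the design effect. Recruitment or follow-up would then go on after someone has seen the result.

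**4. Illustration of the effect (the shift is assumed; nothing in the documents supports a value).** Suppose there is no true effect, but second-half answers move by b points in favor of a device. The final contrast moves by b/2. With 50 per arm, SE = 11.8 × √(2/50) = 2.36, and the 0.016 threshold is |z| > 2.409. For b = 2 the shift is 1 / 2.36 = 0.424 SE, and rejection = [1 − Φ(1.985)] + Φ(−2.833) ≈ 0.0236 + 0.0023 = 0.026.

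| Assumed shift b | Shift in final contrast | Rejection, SD 11.8 | Rejection, SD 16.7 |
|---|---|---|---|
| 0 | 0 | 0.016 | 0.016 |
| 1 | 0.5 | 0.018 | 0.017 |
| 2 | 1.0 | 0.026 | 0.021 |
| 3 | 1.5 | 0.039 | 0.027 |
| 5 | 2.5 | 0.089 | 0.049 |

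The SD of 16.7 is 11.8 × √2, an assumed SD for a change score.

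**5. How much data would still be open to influence?** Section I, item 2 allows eight months for recruitment and follow-up, and each patient is followed for six, which leaves 8 − 6 = 2 months to recruit. With even accrual (an assumption), 50% enrollment falls at about month 1, before any patient reaches day 90. Earlier KCCQs at clinic visits are allowed, so an interim could still be computed. If instead it waits for day 90 in the first 100 patients, it falls at about month 1 + 3 = 4. The other 100 or so would then give their day-90 KCCQ between months 4 and 5, and most day-180 questionnaires would follow. The plan does not say which reading is meant.

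**The case against.** A reader might infer that the remaining KCCQ will be collected by a team that knows the trend. The documents do not support that. They call the interim internal and say no more: nobody is named to run it, no recipient is named, and nothing says coordinators, clinicians or patients will be told.

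Some routes that come to mind are also weak. Coordinators and providers are trained before the study starts, so training cannot carry an interim result. Coaching comes from the products, not from the investigators. The KCCQ is a standardized 23-question instrument completed mainly electronically, which limits, though it does not remove, a coordinator's influence. Staff already know allocation, so reporting bias exists without any interim, and the interim can only add to it. If the look really falls at 50% enrollment on the accrual assumed above, there may be no day-90 result to leak.

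A reader might also infer that the technology partner will see efficacy by arm. Section I, item 11 says "We plan to share non-aggregate de-identified data with Medullan", with periodic transfers, but does not say that these contain KCCQ by arm.

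All of this stands, and it limits the point to a preventable risk of unknown size. It does not remove the gap. An efficacy look described as internal, in a trial where the investigators decide on analysis and the principal investigator can stop the study, leaves access open by default. Encouragement, alert triggers and assisted survey completion all remain adjustable after the look. The argument that minimal risk needs no monitoring committee is fair, but none is asked for, because the issue is validity rather than safety.

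**Conclusion.** The point holds as a cheap improvement. The plan provides neither independent conduct of the interim efficacy analysis nor any limit on access to its result, in an unblinded trial with a patient-reported primary endpoint.

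The stronger statement, that the study team will know the trend, goes beyond the text. So would any claim that the thresholds are wrong: they spend about 0.0162 per comparison and control alpha.

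The size of any bias cannot be computed from the documents. The rise from 0.016 to about 0.026 (0.021 with SD 16.7) rests on an assumed 2-point shift in half the data, 50 per arm, no true effect and a two-sided test. It shows sensitivity and is not an estimate. How much data would be exposed depends on which records enter the interim, which the plan leaves open.

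**What to change.** In Section I, items 12 and 13, replace the internal look with the following:

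- **Who.** The independent statistician already named for the randomization lists runs the interim.
- **On what.** State the data set, for example patients with a day-90 KCCQ.
- **What is returned.** Only whether p < 0.0006 is crossed for each of the three device-versus-control comparisons. Reporting each one matters because the plan does not say how three comparisons become one decision to stop.
- **What is withheld.** KCCQ-by-arm results, and any partner transfer that contains KCCQ by arm, are kept from investigators, coordinators and partners until the last day-90 KCCQ is collected.
- **What is unchanged.** The principal investigator keeps full access to safety data (deaths, admissions, ED visits, adverse events), so the safety reviews in item 12 go on as planned.

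Sample size, alpha, boundaries and patient care do not change. The cost is a small added task, with data access, for that statistician, and investigators and partners wait longer for efficacy results. Two limits remain. Staff still know allocation, and day-180 answers given after release are not protected, although those serve a secondary analysis.

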(Descriptive	number of page views, origin of login (direct, email))				
(Descriptive statistics)	number of page views, origin of login (direct, email)) Average number of interactions				
· ·					
• •	Average number of interactions				
· ·	Average number of interactions Average number of daily check-ins				
· ·	Average number of interactions Average number of daily check-ins Number of patients not using product per week				

We will also perform prespecified secondary analyses to determine the above primary and secondary outcomes at day 180, to determine if outcomes improve once clinic visits end.

An additional secondary analysis will assess the heterogeneity of the effect of each product across clinics.

5. Genetic Testing N/A 🛛

6. **Subject Population:** Provide a detailed description of the types of human subjects who will be recruited into this study.

This study will enroll adult patients attending one of the nine clinics located within YNHHS specializing in the treatment of heart failure, for management of congestive heart failure. See inclusion and exclusion criteria below.

7. **Subject classification:** Check off all classifications of subjects that will be specifically recruited for enrollment in the research project. Will subjects who may require additional safeguards or other considerations be enrolled in the study? If so, identify the population of subjects requiring special safeguards and provide a justification for their involvement.

□Children	🗆 Healthy	□Fetal material, placenta, or dead fetus
□Non-English Speaking	Prisoners	Economically disadvantaged persons
Decisionally Impaired	Employees	□Pregnant women and/or fetuses
□Yale Students	□ Females of childbearing pote	ential

NOTE: Is this research proposal designed to enroll children who are wards of the state as potential subjects? Yes □ No ⊠

8. Inclusion/Exclusion Criteria: What are the criteria used to determine subject inclusion or exclusion? Inclusion Criteria:

- 1. Adults \geq 18 years and < 80 years of age
- 2. Enrolled in a YNHHS clinic specializing in heart failure treatment
- 3. Diagnosed with congestive heart failure (CHF) (preserved ejection fraction (HFpEF) or reduced ejection fraction (HFrEF)) with or without diabetes
- 4. Within one month of a clinic visit

Exclusion Criteria:

- 1. Class IV heart failure
- 2. Stage 4 or end stage renal disease (eGFR < 30)
- 3. Recipient of a heart transplant or ventricular assist device
- 4. Under hospice care
- 5. Dementia

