The study was designed to provide adequate power to detect a clinically significant change in the primary outcome measure, the score on the Kansas City Cardiomyopathy Questionnaire.⁸

The 23-item questionnaire has been validated in multiple heart failure populations, and quantified the physical limitations, symptoms, self-efficacy, social interference, and quality of life associated with living with heart failure. The KCCQ composite score can theoretically range from 0 - 100 (with 100 being the best possible score) and a change of 10 points has been determined to be the minimum clinically important difference. Within a given patient, the score is quite stable in the absence of clinical changes, with a within-patient standard of deviation of 11.8 for patients with no change in clinical status.⁹

In order to detect the minimum clinically important difference of a 10-point improvement in the KCCQ, we would need to enroll 40 patients in each arm of the trial across all centers to provide 90% power at an alpha threshold of 0.017. This gives a total of enrollment of 160. Given uncertainties around the intraclass correlation coefficient (assumed to be 0.10 here and reflecting the overall efficacy of each individual clinic) we will inflate the target sample size to 200, or 50 per arm of the trial. The lower alpha threshold represents a bonferonni correction that provides statistical power to test multiple comparisons – each of the 3 digital health interventions against the control intervention. We will attempt to balance recruitment across the centers with a per-center target of 5 individuals per trial arm.

An interim analysis will be completed at 50% enrollment. We will stop the trial for efficacy for a p value threshold of < 0.0006. Given the interim analysis, the threshold p-value for statistical significance at the end of the trial will be 0.016.

The primary analysis will be a mixed effects model comparing change in KCCQ over time in the intervention group versus the control, without accounting for a center-by-treatment interaction. In secondary analyses, we will model that interaction to determine if certain interventions are uniquely effective in certain centers.

Secondary and exploratory analyses will examine the outcomes listed above using the same procedure applied to baseline variables for outcomes assessed at one time point, and using mixed-effects models for continuous outcomes assessed at multiple timepoints.

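### The 90% power at 40 per arm appears to rest on an SD of 11.8 from clinically unchanged patients; for between-arm change in KCCQ under active management it is unsupported, and the documents do not settle whether 50 per arm restores it

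*Combined protocol and SAP*

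**What the plan says.** All of the sample-size reasoning is in Section I, item 13 (Statistical Considerations). It takes 10 points on the KCCQ as the minimum clinically important difference and describes the score as stable, "with a within-patient standard of deviation of 11.8 for patients with no change in clinical status". It then says that the trial would "need to enroll 40 patients in each arm of the trial across all centers to provide 90% power at an alpha threshold of 0.017". The alpha is a Bonferroni share for three comparisons, each device against control. No sidedness, dropout rate, SD of change or baseline-to-follow-up correlation is given.

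The total is then raised from 160 to 200, or 50 per arm. The reason given is "Given uncertainties around the intraclass correlation coefficient (assumed to be 0.10 here and reflecting the overall efficacy of each individual clinic"). After the planned interim look, "the threshold p-value for statistical significance at the end of the trial will be 0.016".

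On the analysis, the same item says: "The primary analysis will be a mixed effects model comparing change in KCCQ over time in the intervention group versus the control". That model is to be fitted "without accounting for a center-by-treatment interaction". Section I, item 4 (Outcomes) makes 90 days the primary time point and schedules the KCCQ at baseline, day 90 and day 180. Under Patient Follow-Up and Data Collection, the first three months are a period of active management with visits every 2-3 weeks. Under Subject Eligibility and Recruitment, the plan notes that some patients' care may not yet be optimised.

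**The concern.** The SD that drives the power has to be the SD of the quantity compared between arms. Here that is change in KCCQ to day 90, or day-90 KCCQ adjusted for baseline, in patients whose treatment is being actively managed. The documented 11.8 describes score variation within patients whose condition did not change. That is a different quantity, for two reasons:

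- **True change varies between patients.** Some will improve under management and some will not. An SD from unchanged patients excludes this spread by construction.
- **What 11.8 measures is not stated.** It could be the SD of a single score about a patient's own mean, or the SD of a change between two occasions. If it is the former, a contrast between day 90 and baseline also carries the baseline score's own variation.

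At stake is how a non-significant device comparison is read. A reader who trusts the stated power will take the chance of missing a true 10-point benefit to be 10% or less. The protocol does not give enough to confirm that.

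**Working it through.** **Inputs from item 13:** difference 10; SD 11.8; 40 per arm with 90% power at alpha 0.017; 50 per arm planned; final alpha 0.016. **Assumed:** two-sided two-sample t-test, equal arms. Power is taken from the noncentral t distribution with 2n − 2 degrees of freedom and noncentrality 10 / (SD × √(2/n)).

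**1. Reproducing the plan's figure.** With SD 11.8 and n = 40 the noncentrality is 10 / (11.8 × √0.05) = 3.79, and power at alpha 0.017 is 90.9%. The smallest n reaching 90% is 39 at alpha 0.017 and 40 at 0.05/3. A one-sided test with the same SD would need only 34. That 11.8 was the input is an inference, but it is the only SD given and it matches.

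**2. Slack.** Solving for the SD at which power is exactly 90%:

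| Analysed per arm | Alpha | Largest SD keeping 90% |
|---|---|---|
| 40 | 0.017 | 11.97 |
| 40 | 0.016 | 11.89 |
| 50 | 0.016 | 13.35 |

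So the 40-per-arm claim has almost no margin. At 50 per arm the margin is 13.35 / 11.8 = 1.13, or 13%.

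**3. If 11.8 is already an SD of change in stable patients.** Let tau be the SD of true change between patients (assumed; not in the documents). The outcome SD is √(11.8² + tau²). At 50 analysed per arm, alpha 0.016:

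| tau | Outcome SD | Power |
|---|---|---|
| 0 | 11.8 | 96% |
| 5 | 12.82 | 92% |
| 8 | 14.26 | 85% |
| 10 | 15.47 | 78% |

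The 90% survives up to tau = √(13.35² − 11.8²) = 6.2.

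**4. If 11.8 is a single-score SD, with no variation in true change.** Let r be the correlation between any two of a patient's scores (assumed 0.5 to 0.8). At 50 analysed per arm, alpha 0.016:

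| Contrast | Outcome SD | Power |
|---|---|---|
| Day 90 minus baseline, unadjusted | 11.8 × √2 = 16.7 | 71% |
| Day 90, baseline-adjusted | 11.8 × √(1 + r) = 14.5 to 15.8 | 84% to 76% |
| Mean of two post-baseline scores, baseline-adjusted | 11.8 × √(1/2 + r) = 11.8 to 13.45 | 96% to 89% |

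**5. The ICC.** Section I, item 4 (Subject Randomization and Intervention) randomises individual patients from lists stratified by clinic. With arms balanced within clinic and total SD s, the standard error of an arm difference at 50 per arm is s × √(2/50) = 0.200s at ICC 0, and s × √(0.9 × 2/50) = 0.190s at ICC 0.10. A clinic effect common to all arms therefore does not raise the required number.

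**The case against.** The strongest reply is that the trial enrols 50 per arm, not 40, and that 50 keeps 90% up to an SD of 13.35. That stands, and it is why the 90% is called unsupported and not false. But the plan assigns the increase to the ICC, not to uncertainty in the SD or to dropout, so it cannot be read as a considered allowance for either.

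A second reply is that the mixed model may use more than one follow-up score. The KCCQ is scheduled at days 90 and 180, and the follow-up section also has coordinators giving it at clinic visits. This stands in part. If two post-baseline scores are averaged, the single-score reading need not give an SD above 11.8. The primary time point is still day 90, however, and the averaging does not restore the variation in true change left out on either reading.

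Three stronger conclusions are tempting, and the documents do not support them:

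- **That the trial is underpowered, at 71% or thereabouts.** That figure needs 11.8 to be a single-score SD, one follow-up score and no baseline adjustment. None of these is stated.
- **That the ICC is simply a wrong reason for 50 per arm.** It fails only if the clinic effect is common to all arms. The plan's wording refers to each clinic's efficacy, and secondary analyses will look for device effects that differ by clinic. Leaving that interaction out of the primary model does not remove it from the data.
- **That only 45 per arm will be enrolled.** Patients will be "attending one of the nine clinics located within YNHHS", and recruitment is planned "with a per-center target of 5 individuals per trial arm", so 9 × 5 = 45. But this is a target for balancing recruitment, not a cap, and the enrolment target is 200 throughout.

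Removing clinic variance could also help. At ICC 0.10 and 50 per arm, multiplying the SD by √0.9 lifts power from 81% to 85% at SD 15, and from 71% to 76% at SD 16.7.

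**Conclusion.** The arithmetic in the plan is sound; its SD is not shown to fit the planned comparison. The claim of 90% at 40 per arm is unsupported and would fail with an SD only slightly above 11.8. Whether the enrolled 50 per arm deliver 90% at the final alpha turns on whether the true outcome SD is below about 13.35, and the documents do not settle this. Depending on what 11.8 measures and on assumed values of tau and r, the chance of missing a true 10-point benefit at 50 analysed per arm runs from about 4% to about 29%. Those limits are illustrations, not estimates. The single-score figures leave out variation in true change, all figures assume a two-sided test, and none allows for attrition. The point should be fixed because this is the trial's only power statement and it concerns the primary outcome.

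**What to change.** Keep 200 patients and reword the sample-size paragraph:

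1. State whether 11.8 is a single-score SD or an SD of change, that the test is two-sided (if that is the intention), and how baseline and the day-90 contrast enter the mixed model.
2. Replace the single 90% claim with power for a 10-point difference at alpha 0.016 over SDs labelled as assumed, ignoring any gain from removing clinic variance:

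| Assumed outcome SD | 50 analysed per arm | 40 analysed per arm (assumed 20% attrition) |
|---|---|---|
| 12 | 96% | 89% |
| 15 | 81% | 70% |
| 16.7 | 71% | 59% |

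3. State that the ICC justifies the increase to 50 only if treatment effects vary by clinic, because a clinic effect common to all arms cancels under randomisation stratified by clinic. If the extra 10 per arm are meant for attrition or SD uncertainty, say so.

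The cost is a rewritten paragraph and one small table, with no added patients and no change to procedures. The downside is that the stated power becomes less favourable.
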